6.8.3 Analysis of Other Exploratory Efficacy Variables

All the continuous exploratory variables will be analyzed using descriptive statistics (n, mean, median, standard deviation, minimum, and maximum).

All the binary exploratory variables will be summarized with frequency and percentages.

No missing data imputations and sensitivity analysis are applicable for other exploratory endpoints.

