3 STUDY OBJECTIVES AND ENDPOINTS

Study objectives and endpoints are summarized in [Table 3](#) .

Table 3 Study Objectives and Endpoints

Primary Objective	Primary Endpoint
To evaluate AEs emergent from multiple doses of IMG-007 in adult participants with AD	Incidence of TEAEs
Secondary Objectives	Secondary Endpoints
To evaluate the efficacy of multiple doses of IMG-007 in AD participants as measured by EASI at Week 12	Percentage change in EASI from baseline to Week 12
Exploratory Objectives	Exploratory Endpoints
To evaluate the efficacy of multiple doses of IMG-007 in AD participants as measured by EASI, IGA, SCORAD index, and patient-assessed itch and sleep quality NRS, PGIS of AD, PGIC of AD, and DLQI	
 Mean and mean % change from baseline in EASI by visit Proportion (%) of participants achieving EASI-50 by visit Proportion (%) of participants achieving EASI-75 by visit Proportion (%) of participants achieving EASI-90 by visit Mean change from baseline in IGA by visit Proportion (%) of participants achieving IGA 0 or 1 (clear or almost clear) and \geq 2-point reduction from baseline by visit Proportion (%) of participants achieving \geq 2-point reduction in IGA from baseline by visit Change from baseline in percent BSA by visit Change from baseline in SCORAD by visit Mean and mean % change from baseline in WI-NRS by visit Proportion (%) of participants achieving a \geq 4-point reduction from baseline in WI-NRS by visit in participants with WI-NRS \geq 4 at Baseline Mean and mean % change from baseline in SQ-NRS by visit Change from baseline in PGIS by visit Proportion (%) of participants with PGIS of 0 or 1 by visit Proportion (%) of participants reporting PGIC of “much better” or “a little better” by visit Change from baseline in DLQI by visit Proportion (%) of participants achieving \geq 4-point reduction from baseline in DLQI by visit in participants with DLQI \geq 4 at Baseline
To further characterize safety and tolerability of multiple doses of IMG-007 in AD participants	
 Incidence of TEAEs by severity and relationship to study treatment Changes from baseline in laboratory parameters, vital signs and ECG parameters by visit Incidence of clinically significant abnormal values in laboratory and ECG parameters by visit

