11.3.3 Analysis of Efficacy Endpoints

Continuous efficacy variables will be summarized using descriptive statistics which will include mean, median, minimum, maximum, Q1 and Q3, standard error and standard deviation. Categorical efficacy variables will be summarized by frequency and percentage for each category.

While the primary comparison of interest for efficacy endpoints will be within Cohort 2, for IMG-007 [REDACTED] versus placebo group, a broader comparison including 300 mg group versus placebo and the combined 300 mg and [REDACTED] versus placebo are also of additional, exploratory interest. For analysis within Cohort 1 (i.e., 300 mg group), efficacy comparison with baseline at each visit will be performed based on difference relative to zero. All analysis will use nominal two-sided significance level of 0.05.

For continuous efficacy endpoints, a mixed-effect model with repeated measures (MMRM) will be used. This model includes visit as a factor and respective baseline score as covariate for both Cohorts 1 & 2, and additionally treatment and treatment-by-visit interaction as factors for Cohort 2 only. [REDACTED]

[REDACTED]
[REDACTED]
[REDACTED]
[REDACTED]
[REDACTED]
[REDACTED]
[REDACTED]

Sensitivity analysis using other missing data handling approaches will also be performed. Further details including handling of specific intercurrent events and missing data imputations will be specified in the prospective statistical analysis plan (SAP).

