11.3.6 Analysis of Exploratory and Other Endpoints

Analyses of exploratory endpoints listed in [Section 3](#) will be generally similar to the primary and secondary analyses, which will be detailed in the SAP.

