1. OVERVIEW

The purpose of the statistical analysis plan (SAP) is to ensure the credibility of the study results by pre-specifying statistical approaches for the analysis of this study. The SAP is intended to be a comprehensive and detailed description of strategy and statistical techniques to be used to realize the analysis of data for IMG-007-201. This SAP was written and finalized prior to the database lock, based on study protocol IMG-007-201 Version 6.0 (05Feb2024). Any methodological deviations from the protocol are documented. The analyses laid out in this SAP will be implemented by MeDaStats LLC for Inmagene Biopharmaceuticals.

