4.5.2.2 Other Exploratory Endpoints

Other exploratory efficacy endpoints are:

- Change from baseline in percent body surface area (BSA) by visit
- Change from baseline in PGIS by visit
- Proportion (%) of participants with PGIS of 0 or 1 by visit
- Proportion (%) of participants reporting PGIC of “much better” or “a little better” by visit
- Change from baseline in DLQI by visit
- Proportion (%) of participants achieving \geq 4-point reduction from baseline in DLQI by visit in participants with DLQI \geq 4 at baseline

Body Surface Area (BSA)

The BSA assessment estimates the extent of disease or skin involvement with respect to AD and is expressed as a percentage of total body surface. BSA will be determined by the investigator using the rule of nines.

Participant will undergo this assessment at selected scheduled clinic visits.

Patient Global Impression of Severity (PGIS) of AD

At the scheduled clinical visits, participants will rate the severity of their AD over the past week on a 5-point scale ranging from 0 = “none” to 4 = “very severe”.

Patient Global Impression of Change (PGIC) of AD

At the scheduled clinical visits, participants will rate the change in their AD on a 5-point scale ranging from 1 = “much better” to 5 = “much worse”. Participants will be asked to provide this rating in comparison to just before the participant started taking study treatment.

Dermatology Life Quality Index (DLQI)

The DLQI is a validated 10-question instrument used to measure the impact of skin disease on the quality of life (QoL) of an affected person over the previous week. The ten questions cover the following topics: symptoms, embarrassment, shopping and home care, clothes, social and leisure, sport, work or study, close relationships, sex, and treatment (Finlay, Khan. 1992). The DLQI score ranges from 0 (no impact of skin disease on QoL) to 30 (maximum impact on QoL).

The DLQI is completed by the participant in the study clinic. Assessments will be recorded in the eCRF.

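### SAP 6.8.3 drops the protocol's MMRM for change in BSA, PGIS and DLQI without recording it, which leaves late-visit means exposed if dropout is related to response

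*SAP*

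**What the plan says.** - Protocol 11.3.3, and the synopsis in the same words: "For continuous efficacy endpoints, a mixed-effect model with repeated measures (MMRM) will be used". For Cohort 1 the model has visit as a factor and baseline score as covariate, and each visit is compared with baseline. The section also promises: "Sensitivity analysis using other missing data handling approaches will also be performed".
- Protocol 11.3.6, on exploratory endpoints: their analyses "will be generally similar to the primary and secondary analyses, which will be detailed in the SAP".
- Protocol section 3 (Table 3) puts "Change from baseline in percent BSA by visit", and change in PGIS and DLQI, in one exploratory list with EASI, IGA, SCORAD and the itch and sleep scales. The list has no tiers.
- The SAP splits that list in two. The key tier (4.5.2.1) holds EASI, IGA, SCORAD and the two NRS scales, and 6.8.2.1 analyses its continuous endpoints with the MMRM of 6.8.1. The other tier (4.5.2.2) holds "Change from baseline in percent body surface area (BSA) by visit" and change in PGIS and DLQI.
- SAP 6.8.3, for the other tier: "All the continuous exploratory variables will be analyzed using descriptive statistics (n, mean, median, standard deviation, minimum, and maximum"). It rules out imputation and sensitivity analysis.
- SAP section 1: "Any methodological deviations from the protocol are documented". SAP section 5 and the SAP version history record only the removal of Cohort 2.

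**The concern.** Three endpoints that the protocol places under the MMRM lose the model, the comparison with baseline and any confidence interval. SAP 6.8.3 also omits the standard error and quartiles that protocol 11.3.3 lists for continuous efficacy variables. The section that should record such a change is silent.

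The practical issue is missing data. A mean over the participants observed at a visit is unbiased only if absence is unrelated to outcome. An MMRM also uses the earlier visits of those who left, and so remains valid when leaving depends on scores already seen. BSA and DLQI would therefore be reported on a different missing-data footing from EASI and SCORAD in the same 13 people, with nothing in the SAP to say so. Protocol 4.1 says that Cohort 1 is expected to inform the design of a Phase 2b study, so a reader may well set these results side by side.

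**Working it through.** **1. The texts side by side**

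| Item | Current protocol | SAP |
|---|---|---|
| EASI, IGA, SCORAD, NRS change | MMRM (11.3.3) | MMRM (6.8.1, 6.8.2.1) |
| BSA, PGIS, DLQI change | MMRM (11.3.3); broadly similar methods (11.3.6) | Descriptive only (6.8.3) |
| Missing-data sensitivity analysis | Promised (11.3.3) | Ruled out for the other tier (6.8.3) |
| Departure recorded | not applicable | Not in section 5 or the version history |

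The documents state no effect size, SD or dropout rate for these endpoints, so there is no planned figure to reproduce. Steps 2 to 4 rest on assumed inputs and show direction and order of size only.

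**2. Arithmetic with n = 13 (protocol 4.1)**

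Assume that those who stay change by -8 DLQI points and that k leavers change by 0. The observed mean is -8.0 whatever k is. The mean over all 13 is -8 × (13 - k)/13:

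- k = 1: -7.4
- k = 2: -6.8
- k = 3: -6.2

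The overstatement is 0.6, 1.2 and 1.8 points.

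**3. Simulation in 13 participants**

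DLQI at Weeks 4, 8, 12, 16, 20 and 24 (schedule of assessments). Assumed: true change -6, SD 6, constant correlation 0.7. A participant who has improved by less than 4 points at a visit leaves before the next with the probability shown. The comparator is a random-intercept model with visit as a factor; 400 replicates.

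| Exit probability | Missing at Week 24 | Error of observed mean | Error of mixed model | SD of observed mean |
|---|---|---|---|---|
| 0.1 | 16% | -0.85 | -0.07 | 1.71 |
| 0.2 | 28% | -1.66 | -0.12 | 1.95 |
| 0.3 | 37% | -2.11 | -0.01 | 1.91 |

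As a share of the assumed effect this is 0.85/6 = 14%, 1.66/6 = 28% and 2.11/6 = 35%. In units of the standard error it is 0.85/1.71 = 0.5, 1.66/1.95 = 0.9 and 2.11/1.91 = 1.1. Further sets of 300 and 200 replicates put the observed-mean error at 0.86 to 1.0, 1.6 to 1.7 and 2.25 to 2.3. In the set of 300 the mixed-model error reached 0.16.

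Two variations reduce the error of the observed mean:

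- If each leaver contributes one further assessment, as a completed withdrawal visit would, it falls to 0.6, 1.1 and 1.7 points.
- With exit probability 0.05 (7 to 9% missing, about one person in 13), it is 0.2 to 0.4 points, or 0.1 to 0.2 standard errors.

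**4. Large-sample check with an unstructured model**

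200,000 simulated participants, the same six visits. Assumed: true Week 24 change -7, SD 6, correlation constant at 0.5 or 0.7, or AR(1) at 0.8. The comparator is the likelihood estimate of the visit mean under an unstructured normal model. Leaving depends on the last observed score:

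| Missing at Week 24 | Observed mean | MMRM-type estimate |
|---|---|---|
| 10% | -7.4 to -7.6 | -7.0 |
| 20% | -7.8 to -8.1 | -7.0 |
| 30% | -8.2 to -8.6 | -7.0 |
| 40% | -8.6 to -9.1 | -7.0 |

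If leaving depends on the score that is never seen, both are biased across 10 to 40% missing: -7.5 to -9.4 for the observed mean and -7.2 to -8.0 for the MMRM-type estimate. If leaving is unrelated to response, both give -7.0.

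**The case against.** **The protocol delegates the detail.** Section 11.3.6 asks only for general similarity and leaves the rest to the SAP, and 11.3.3 itself plans descriptive summaries. A split into key and other tiers falls within that latitude. Removing the model, the confidence interval and the comparison with baseline does not: what remains is no longer similar to the primary and secondary methods.

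**The versions differ.** SAP 2.0 (17 May 2024) cites protocol V6.0 (05 Feb 2024), while the supplied protocol is dated 14 June 2024. A reader might infer a proven departure from the text that the SAP was written against. That cannot be shown, because the V6.0 wording is not available. What can be shown is that the current documents disagree.

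**Thirteen people are few for an MMRM.** BSA is scored as part of SCORAD, which has nine post-baseline visits, so an unstructured matrix through Week 24 has 9 × 10/2 = 45 parameters. This stands as a warning that the fallback will probably be needed. It does not separate these endpoints from SCORAD or IGA, which have the same visits in the same people and keep the MMRM. PGIS is a 5-point item for which descriptive statistics are defensible, but so is IGA.

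**The mixed model may look better than it is.** A reader might infer from step 3 that it is accurate to about 0.1 point. That result comes from a random-intercept model fitted to data with a matching correlation pattern. With AR(1) 0.8 data the same model erred by 0.2 to 0.5 point in the other direction (Monte Carlo error about 0.14). Nor is it the SAP's model, which adds a baseline covariate, an unstructured matrix and Kenward-Roger degrees of freedom.

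**Attrition is limited and would be visible.** Participants who stop treatment stay in follow-up, those who withdraw are asked for a final visit (unless lost to follow-up or withdrawing consent), and n is already part of the planned summaries. All of this reduces the concern.

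**Conclusion.** The inconsistency between the current protocol and the SAP is plain from the text, and the SAP does not record it. The consequence for the estimates is conditional. If poor responders withdraw, late-visit observed means overstate improvement, and an MMRM would largely correct this when dropout depends on observed scores.

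A reader might infer that the SAP's choice biases results in the drug's favour. The documents do not support that: they give no dropout rate, reason or direction. With dropout unrelated to response there is no bias, and if good responders left, its sign would reverse. It is also not certain exactly which values enter the means, because the intercurrent-event handling is redacted and SAP section 6 allows n to include values set by that handling.

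The illustrative size is about 0.2 to 2 DLQI points over roughly 8 to 37% missing at Week 24. It rests wholly on the assumed mean, SD, correlation and exit rule, and is smaller if withdrawal visits are completed. Severity is minor: these are exploratory endpoints in 13 open-label participants without a control group. The primary safety endpoint and Week 12 EASI are unaffected.

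**What to change.** In SAP 6.8.3, state that change from baseline in BSA and DLQI, and in PGIS on the same footing as IGA, will be analysed with the MMRM of 6.8.1 and 6.8.2.1, including its covariance fallback. Report LS means and 95% confidence intervals by visit, and keep the descriptive tables as support. Name the endpoints in 6.8.2.1 and 6.8.3, since both sections speak of all continuous exploratory variables and only their headings tell them apart.

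If the sponsor prefers descriptive statistics alone, record the departure from protocol 11.3.3 and its reason in SAP section 5.

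The cost is three more endpoints run through a model that is already specified; because 6.8.2.1 uses one model to Week 12 and another to Week 24, that is 3 × 2 = 6 fits. Late-visit improvements may come out slightly smaller. The alternative costs one entry in section 5.

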While the primary comparison of interest for efficacy endpoints will be within Cohort 2, for IMG-007 [REDACTED] versus placebo group, a broader comparison including 300 mg group versus placebo and the combined 300 mg and [REDACTED] versus placebo are also of additional, exploratory interest. For analysis within Cohort 1 (i.e., 300 mg group), efficacy comparison with baseline at each visit will be performed based on difference relative to zero. All analysis will use nominal two-sided significance level of 0.05.

For continuous efficacy endpoints, a mixed-effect model with repeated measures (MMRM) will be used. This model includes visit as a factor and respective baseline score as covariate for both Cohorts 1 & 2, and additionally treatment and treatment-by-visit interaction as factors for Cohort 2 only. Specific ways of handling data after receiving rescue medication or any other such clinical events will be performed.

For binary efficacy endpoints, if high potency corticosteroids or systemic rescue medications are used, the participant will be reported as a non-responder from the time such rescue medication is used.

Sensitivity analysis using other missing data handling approaches will also be performed. Further details including handling of specific intercurrent events and missing data imputations will be specified in the prospective statistical analysis plan (SAP).

PK Analyses

Serum concentration data will be tabulated and summarized (geometric mean, arithmetic mean, minimum, maximum, SD and % coefficient of variation) by treatment group for each visit at which samples were taken.

Immunogenicity Analyses

The immunogenicity results will be summarized using descriptive statistics by the number and percentage of participants who develop detectable ADA. The incidence of positive ADA will be reported for evaluable participants.

PD Analyses

Biomarker data will be listed by participant and visit/timepoint. Data for skin punch biopsy will be listed and summarized by visit.

Timing of Analyses

Timing of Analyses

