5. CHANGES TO PLANNED ANALYSIS FROM PROTOCOL

Screening and enrollment for the placebo-controlled cohort 2 of the study were terminated by sponsor following the communication letter titled 'Enrollment Communication' dated 18Mar2024. Consequently, the study now comprises only one treatment group (IMG 300 mg). Henceforth, all analyses and result reporting will involve only one treatment group. Analyses related to the placebo-controlled cohort (i.e., cohort 2) are no longer applicable and this will not be reported.

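### SAP 6.8.3 neither applies nor cross-refers to the protocol's non-responder-after-rescue rule for the PGIS, PGIC and DLQI responder endpoints, and SAP Section 5 declares no departure

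*SAP*

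**What the plan says.** **Protocol, 1.1 Synopsis (Efficacy Analyses).** The rule begins "For binary efficacy endpoints, if high potency corticosteroids or systemic rescue medications are used", and its consequence is that "the participant will be reported as a non-responder from the time such rescue medication is used". It makes no exception for exploratory endpoints. The synopsis leaves further detail on intercurrent events to the SAP. Protocol Section 3 lists the PGIS, PGIC and DLQI responder endpoints under the exploratory efficacy objective.

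**SAP 4.5.2.2.** Three binary endpoints are classed as other exploratory:
- "Proportion (%) of participants with PGIS of 0 or 1 by visit"
- "Proportion (%) of participants reporting PGIC of “much better” or “a little better” by visit"
- a DLQI reduction of at least 4 points, among participants with a baseline DLQI of at least 4.

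**SAP 6.8.3.** This is the analysis section for that group, and it shows no redaction. For binary variables its instruction is "All the binary exploratory variables will be summarized with frequency and percentages". It then says that missing-data imputation and sensitivity analysis do not apply. It does not mention rescue, 6.8.2.2 or Appendix 12.7.

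**SAP 5.** The only change from protocol concerns the dropped cohort: "Analyses related to the placebo-controlled cohort (i.e., cohort 2) are no longer applicable and this will not be reported". SAP Section 1 says that methodological deviations from the protocol are documented.

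**The concern.** A participant can receive rescue and still complete questionnaires. Protocol 6.9.3 has study treatment stopped after prohibited systemic rescue, but 6.10.1.1 says that stopping treatment is not withdrawal from the study. The last infusion is on Day 29 and visits run to Day 169, so much of the time in which rescue could occur falls after dosing has ended.

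Someone who improves on systemic corticosteroids may then report improvement on PGIC or gain 4 DLQI points. Under the protocol rule that person is a non-responder from the first such rescue. A programmer working from 6.8.3 alone would tabulate the recorded answer.

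Any error runs one way: patient-reported responder rates could include benefit that came from rescue. In an open-label single arm there is no control group against which to separate that benefit from the effect of IMG-007, and the protocol (4.1) expects Cohort 1 to inform a Phase 2b design.

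**Working it through.** The documents state no figure on this point, so there is none to reproduce. The check compares texts and then adds a calculation of scale.

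**1. Does the protocol rule reach these endpoints?** Yes. The synopsis applies it to binary efficacy endpoints in general, and Protocol Section 3 lists the three responder proportions under an efficacy objective.

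**2. Does the readable SAP apply it to them?**

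| SAP section | Endpoints | Rescue handling in readable text |
|---|---|---|
| 6.8.1 | % change in EASI (secondary) | Own heading; content redacted; points to Appendix 12.7 |
| 6.8.2.1 | Continuous key exploratory | Same approach as the main EASI analysis |
| 6.8.2.2 | Binary key exploratory | Own heading; content not visible |
| 6.8.3 | PGIS, PGIC, DLQI, BSA (other exploratory) | No heading, no cross-reference, no redaction |

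**3. Does the no-imputation sentence in 6.8.3 settle it?** No. SAP 6.8.2.2 handles intercurrent events first and missing data second. Ruling out imputation therefore says nothing about rescued participants whose data were observed.

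**4. Does the general text in SAP Section 6 settle it?** Not by itself. It says that the denominators of efficacy percentages depend on intercurrent-event handling set out in later sections. That sentence concerns denominators, and the later section for these endpoints sets out no handling.

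**5. Is a departure declared?** No. Section 5 covers only the loss of Cohort 2.

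**6. Scale.** Inputs:
- n = 13 enrolled (Protocol 4.1). This is an upper bound on the denominator.
- k = number of rescued participants recorded as responders at a visit. The documents do not give it, so k = 1 to 3 is assumed.
- n = 10 for the DLQI subset is assumed, to show the effect of a smaller denominator.

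Shift in the responder percentage = 100 × k/n.

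| k | n = 13 | n = 10 (assumed) |
|---|---|---|
| 1 | 7.7 points | 10.0 points |
| 2 | 15.4 points | 20.0 points |
| 3 | 23.1 points | 30.0 points |

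Illustration with assumed counts: 8 of 13 report improvement and 2 of the 8 had qualifying rescue. Exact (Clopper-Pearson) 95% limits are the 0.025 quantile of Beta(x, n − x + 1) and the 0.975 quantile of Beta(x + 1, n − x).
- Tabulated as recorded: 8/13 = 61.5% (31.6 to 86.1).
- Under the protocol rule: (8 − 2)/13 = 6/13 = 46.2% (19.2 to 74.9).

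The intervals only show how imprecise these rates are; 6.8.3 does not plan any.

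**The case against.** The strongest reply is that silence in one section is not a departure. Section 6 says that efficacy percentages depend on intercurrent-event handling and exempts no endpoint group. The heading in 6.8.2.2 refers generically to responder-type binary endpoints. Appendix 12.7 deals with intercurrent events and is fully redacted. Section 1 says deviations are documented, and none on rescue is listed, so the protocol rule may simply be meant to carry over.

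Much of this stands. A reader might infer that the SAP has no rescue rule for these endpoints and does count rescued improvers as responders. The documents do not support that, because redacted text cannot be treated as absent and 6.8.3 never says that data are taken as observed. A reader might also infer that patient-reported and investigator-assessed rates will follow different rescue rules. That cannot be confirmed either, since the content of 6.8.2.2 is not visible.

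The gap at the point of use remains. The 6.8.2.2 block sits under the key exploratory variables, the visible pointer to 12.7 is in 6.8.1, and 6.8.3 gives an analyst no link to either. If the protocol rule is meant to apply, 6.8.3 should say so.

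It is also fair that rescue use and its duration are summarised and listed under SAP 6.3. Readers can therefore see that rescue happened, although the responder percentages would not be corrected for it.

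**Conclusion.** The point holds as an unresolved inconsistency between the protocol's general rule and the readable SAP text for three binary endpoints. Unless Appendix 12.7 already covers them, following 6.8.3 would count participants who were rescued, remained under observation and reported improvement as responders, with no departure declared.

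Each such participant shifts a by-visit rate by 7.7 points at n = 13, and by more with a smaller denominator. The actual shift is unknown because the number rescued is not given; if nobody had qualifying rescue, it is zero.

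The conclusion assumes that the rescue sentence also stood in the protocol version the SAP was written from. The SAP cites Version 6.0 of 05Feb2024, whereas the protocol reviewed here is dated 14 June 2024.

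A reader might extend the point to mean change in PGIS, DLQI and BSA and ask for the 6.8.1 handling there. The documents do not support that: the quoted rule concerns binary endpoints, and the 6.8.1 handling is redacted.

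This is a minor correction. It touches descriptive exploratory summaries in an open-label cohort of 13 and leaves the primary and secondary endpoints alone.

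**What to change.** Add one sentence to SAP 6.8.3: the PGIS 0/1, PGIC improvement and DLQI 4-point responder endpoints follow the protocol rule, with non-response from the first high-potency corticosteroid or systemic rescue onward. If Appendix 12.7 already says this, a cross-reference is enough. A labelled as-observed row is an optional addition.

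If as-observed tabulation is what the sponsor wants, list it in Section 5 as a deviation from the protocol and give the reason.

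The cost is small: one sentence, plus a dated flag for qualifying rescue, which can be built from the rescue-medication data already summarised under SAP 6.3. No new data are needed. The downside for the sponsor is that patient-reported responder rates may be lower.

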6. STATISTICAL METHODS

For continuous variables, at the reported visits or in overall summary, descriptive statistics will consist of number of participants with observations (n), mean, median, standard deviation (SD),

minimum, and maximum. It is noted that number of participants with observations could include participants with data that were observed as well as those that were imputed for specific types of missing data or determined based on handling of intercurrent events, as explained in later sections.

For categorical variables, frequencies and percentages will be displayed for each category.

In the context of efficacy-related tables, percentages will be calculated based on the denominator of number of participants with data depending on the handling of intercurrent events as well as imputations of missing data as explained in the later sections. For non-efficacy tables, percentages will be calculated based on the corresponding analysis population unless otherwise specified in the mock shell.

Listed below are some subgroups for potential exploratory subgroup analysis:

- Race (Black/African American vs. Non-Black/Non-African American)
- Age group (18-64 years old vs. ≥ 65 years old)
- EASI Score at baseline (EASI ≤ 21 (moderate) and EASI > 21 (severe))
- Disease severity based on IGA score (moderate, defined as IGA at baseline =3 vs. severe, defined as IGA at baseline =4)
- Baseline TARC [REDACTED]
- Age at disease onset (≤ 12 years old vs. > 12 years old)
- Presence of atopic comorbidities (Yes vs. No)
- History of biologics/JAK-I failure

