6.8.2.2 Responder type (binary) efficacy endpoints

The responder type (binary) endpoints will be reported using frequency and percentage along with the 95% Clopper-Pearson exact confidence interval for the proportion. A nominal two-sided 5% significance level will be used.

Based on the estimand framework introduced in [ICH E9 \(R1\)](#), additional details relating to the definition of the estimand is proposed.

Handling of intercurrent events (for responder type binary endpoints) of treatment discontinuation and rescue medication:

Handling of missing data

After the handling of intercurrent events explained above, missing data will be managed in two steps as given below.

- 1) Non-responder imputation will be performed for all scheduled visits following participant discontinuation from the study with the reason 'lack of efficacy'.
- 2) LOCF approach will be applied for all missing visits, except for missing data that arises following study discontinuation with reason 'lack of efficacy'.

Sensitivity analyses

No prespecified sensitivity analyses will be performed. Post-hoc sensitivity analysis will be considered as appropriate later.

Bar plots will be included to depict responder-type of endpoints of EASI and IGA. The X-axis will feature visits, and the Y-axis will represent the proportion of participants, expressed as a percentage.

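### PGIS, PGIC and DLQI responder rates leave out participants who quit the study for lack of efficacy, whereas the EASI, IGA and WI-NRS responder rates count them as failures

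*SAP*

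**What the plan says.** SAP 4.5.2.2 places three responder proportions among the other exploratory endpoints:

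- PGIS: "Proportion (%) of participants with PGIS of 0 or 1 by visit".
- PGIC: the proportion choosing either of the two improvement categories, by visit.
- DLQI: the proportion with a drop of at least 4 points, restricted to those who could achieve it ("in participants with DLQI" of at least 4 at baseline).

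SAP 6.8.3 governs their analysis: "All the binary exploratory variables will be summarized with frequency and percentages". It then adds: "No missing data imputations and sensitivity analysis are applicable for other exploratory endpoints".

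The denominator is set in SAP section 6. For efficacy tables, "percentages will be calculated based on the denominator of number of participants with data depending on the handling of intercurrent events" and on any imputation.

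SAP 6.8.2.2 covers the responder endpoints of the key exploratory tier (EASI-50/75/90, the IGA responders and the WI-NRS 4-point responder). It has two missing-data steps. The first reads "Non-responder imputation will be performed for all scheduled visits following participant discontinuation from the study with the reason" of lack of efficacy. The second carries the last observation forward for every other missing visit.

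**The concern.** The SAP foresees that a participant may leave the study because the drug is not working, and for one tier of responder endpoints it treats that departure as failure. For the other tier, the two rules together (no imputation, divide by those with data) remove the person from both numerator and denominator. The SAP gives no reason for the difference.

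Two consequences follow if such a departure occurs. The PGIS, PGIC and DLQI rates then describe only those who stayed, a group from which known failures have been taken out. And at the same visit, these rates and the EASI, IGA and WI-NRS rates rest on different participants, so they cannot be read side by side. Under SAP section 5 there is now a single treatment group, so no control arm shares the distortion or reveals it. The protocol (section 4.1) expects this cohort to inform the design of a Phase 2b study, so the rates are likely to be used.

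**Working it through.** **Inputs.** N = 13, the number enrolled in Cohort 1 (protocol section 4.1). This is the upper limit for the modified full analysis set, which requires at least one dose (SAP 3.2). The documents give no responder count r and no number d of departures for lack of efficacy, so both are assumptions and are varied. The sample size rests on feasibility, and the plan states no rate to reproduce.

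**Case A: the only missing data come from lack-of-efficacy departures.**

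- SAP 6.8.3 with section 6: rate = r/(N − d).
- SAP 6.8.2.2: rate = r/N.
- Ratio = N/(N − d), which does not depend on r provided r is at least 1.

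Ratios: d = 0 gives 1; d = 1 gives 13/12 = 1.083; d = 2 gives 13/11 = 1.182; d = 3 gives 13/10 = 1.300.

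| Responders r | 6.8.2.2 rule, r/13 | 6.8.3, d = 1 | 6.8.3, d = 2 | 6.8.3, d = 3 |
|---|---|---|---|---|
| 3 | 23.1% | 25.0% | 27.3% | 30.0% |
| 5 | 38.5% | 41.7% | 45.5% | 50.0% |
| 7 | 53.8% | 58.3% | 63.6% | 70.0% |
| 9 | 69.2% | 75.0% | 81.8% | 90.0% |

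For one to three departures, the absolute gap runs from 1.9 to 6.9 points with 3 responders and from 5.8 to 20.8 points with 9. For scale, the Clopper-Pearson 95% interval for 7/13 is 25.1% to 80.8%, so these gaps sit inside wide sampling error. They differ from it in having a known direction.

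**Case B: data missing for another reason.** Suppose 7 of 13 have responded and 2 of those 7 then leave for logistical reasons.

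- 6.8.2.2 (carried forward as responders): 7/13 = 53.8%.
- 6.8.3 (dropped): 5/11 = 45.5%.

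Here 6.8.3 gives the lower figure, so the direction depends on why data are missing.

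**Case C: only the non-responder step with a fixed denominator of 13.** In the Case B situation this gives 5/13 = 38.5%. It is a third rule, stricter than the one used for EASI and IGA, because every other missing visit becomes a failure by default. Matching 6.8.2.2 needs both of its steps.

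**Does the withdrawal visit fill the gap?** Not fully. Early leavers are asked to complete the Week 12 or Week 24 assessments when they withdraw (protocol 6.10.2). SAP 7.3 and Appendix 12.6 assign data by study day where appropriate. If those windows are applied, a withdrawal visit on Day 60 falls in Week 8 and one on Day 100 falls in Week 16, and the later visits stay empty.

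**The case against.** The strongest reply is that the trigger may be rare or absent. Lack of efficacy is a listed reason for stopping study treatment (protocol 6.10.1.1) but is not among the reasons listed for leaving the study (6.10.2). Dosing ends at Day 29, those who stop treatment are asked to keep attending, and rescue is compatible with staying in the study. This stands as a limit on the likely size. It does not remove the point, because SAP 6.8.2.2 itself provides for study discontinuation with that reason.

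Second, some failures may already be counted. The protocol synopsis makes users of high-potency corticosteroid or systemic rescue non-responders for binary efficacy endpoints, and the intercurrent-event text in SAP 6.8.2.2 and Appendix 12.7 is redacted. This also stands in part. The events named in 6.8.2.2 are treatment discontinuation and rescue, and the visible text of 6.8.3 does not say whether any such rule reaches these endpoints.

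Third, observed-case reporting is a common and transparent choice for bottom-tier descriptive endpoints, and SAP 6.6 tabulates discontinuations with reasons. That is fair, and it keeps the point minor. But a disposition table does not give the corrected rate.

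A reader might go further and infer that the reported rates are inflated in fact, that the bias always favours the drug, or that it must grow towards Week 24. The documents support none of these. No dropout is reported, Case B shows the opposite direction, and growth needs such departures to accumulate. Nor are all patient-reported responders affected, since WI-NRS already falls under 6.8.2.2.

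**Conclusion.** The point holds in a conditional form. As written, SAP 6.8.3 with section 6 drops lack-of-efficacy leavers from the PGIS, PGIC and DLQI responder rates, while 6.8.2.2 keeps them as non-responders for EASI, IGA and WI-NRS. The relative overstatement is 8%, 18% or 30% for one, two or three such departures, assuming all 13 were treated, at least one participant responded and nothing else is missing. It is zero if no one leaves for that reason. For DLQI the base is the subset with a baseline score of at least 4, so with fewer than 13 in that subset each such departure from it weighs more. The primary safety endpoint and the secondary EASI endpoint are untouched. This is a cheap improvement to exploratory reporting, not a flaw that threatens the study's conclusions.

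**What to change.** In SAP 6.8.3, apply both missing-data steps of 6.8.2.2 to the binary PGIS, PGIC and DLQI endpoints: non-responder after study discontinuation for lack of efficacy, and last observation carried forward for other missing visits. Use the modified full analysis set as the population and, for DLQI, its members with a baseline score of at least 4. Print the observed-case rate and n per visit beside the result.

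Two details need a sentence each. PGIC has no baseline value, so state what happens when there is no post-baseline rating to carry forward. A DLQI questionnaire with two or more unanswered items is not scored (Appendix 12.5), so say that it is handled as a missing visit.

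The cost is a little extra programming, since the 6.8.2.2 derivation can be reused for three more endpoints, and possibly slightly lower reported rates.
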